## **10.5. Adverse Event Reporting Requirements**

### **10.5.1. Serious Adverse Events**

All events meeting the criteria for SAEs (see [Section 10.4.2](#)) must be reported by investigational sites within 24-hours of becoming aware of the event. The investigator may determine that the event is the natural progression of disease and therefore should be reported as an AE, but not a Serious AE. Some examples are as follows:

- Progression of respiratory failure to require artificial ventilation
- Prolongation of hospitalization due to ventilator-associated pneumonia
- Persistent oxygen requirement lasting beyond hospital discharge

In order to determine the sponsor's timeline for notifying regulatory authorities and investigators per Federal Regulations, an event term, serious criteria, and causality is required at the time of the initial report. Specific SAE reporting instructions are provided in a separate manual.

The investigator is responsible for notifying the IRB/IEC/REB in writing of serious events as soon as is practical in accordance with the policy of the IRB/IEC/REB.

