GC4419 is eliminated by GI and renal routes. Human volunteer studies of GC4419 in the setting of compromised renal or hepatic function are in progress. There has been no apparent nephrotoxicity or hepatotoxicity of GC4419 in human clinical trials.

Rationale for the present study: The pathogenesis of severe-to-critical pulmonary disease complicating SARS-CoV-2 infection—and, when it occurs, the pathogenesis of attendant shock—along with the mechanism and available nonclinical and clinical data with GC4419, suggest that GC4419 could attenuate or reduce the risk of ARDS and the need for mechanical ventilation, and attenuate shock, in people suffering from them due to SARS-CoV-2.

The present study is intended as an initial assessment to confirm the safety of GC4419 in COVID-19 patients with critical respiratory illness. Hospitalized subjects whose respiratory function has deteriorated to the point where mechanical ventilation is needed will be studied. Subjects will be randomized in a 1:1 ratio to receive either GC4419 or placebo plus standard supportive care.

Upon review of results from this trial, future trials to treat COVID-19 patients with GC4419 earlier in the course of disease—e.g., in the setting of worsening hypoxemia and increasing requirement for supplemental oxygen short of mechanical ventilation—may be considered.

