Most significantly, especially in respiratory viral disease, the immune response to extensive infection produces massive  $O_2\cdot^-$  bursts from various monocytic and polymorphonuclear leukocytes. These  $O_2\cdot^-$  bursts may be an essential part of the immune response to viral infection, either for immune cell recruitment or, when further converted to  $H_2O_2$  and hypochlorous acid (HOCl), for direct action against the virus [28,29]. However, when this inflammatory production of  $O_2\cdot^-$  is excessive and prolonged it leads to host cell death and tissue damage [20,23,28,29]. This excessive and prolonged production of  $O_2\cdot^-$  then can become part of a vicious cycle sometimes referred to as cytokine storm, as superoxide not only damages host tissue, but also drives release of pro-inflammatory cytokines such as  $TNF\alpha$ ,  $IL-1\beta$  &  $IL-6$  [16,18,20,23] and other chemottractants at the site. In the process membrane lipid oxidation also occurs, leading to activation of TLR4 and via that of NADPH oxidase (NOX) enzymes which produce even more  $O_2\cdot^-$  [25,28-29]. In turn this exacerbates the hyperactive immune response leading to increased generation of  $O_2\cdot^-$  [28]. For respiratory-targeting viruses this leads to and exacerbates acute lung injury and ARDS.

As  $O_2\cdot^-$  has been shown to drive similar tissue injury and inflammatory damage patterns in other organs [6,30-35] it is possible that similar biology is involved in viral pathologies in these other sites, such as kidney or heart.

By a somewhat different mechanism,  $O_2\cdot^-$  has also been shown to be at least partially responsible for the inability to maintain blood pressure and adequate perfusion in so-called (bacterial) “septic shock” [36-38]. In this situation,  $O_2\cdot^-$  generated by the hyperinflammatory response to septicemia initiates the auto-oxidation of catecholamines such as epinephrine, norepinephrine & dopamine, leading to self-perpetuating refractory hypotension. In animal models of LPS and live bacteria-induced refractory hypotension, the oxidation of the catecholamines produces a characteristic set of toxic end-products, adrenochromes [36], which a clinical observation study also strongly correlated to the presence of septic shock [39]. While some case reports suggest a similar refractory hypotension, it is unclear whether this is an issue for many critically ill COVID-19 patients.

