#### **10.4.2. Serious Adverse Event (SAE)**

Any untoward medical occurrence that at any dose:

- Results in death,
- Is life-threatening – *NOTE: The term 'life-threatening' in the definition of 'serious' refers to any adverse drug experience [adverse event] that places the patient or subject, in the view of the investigator, at immediate risk of death from the reaction as it occurred, ie, it does not include a reaction that, had it occurred in a more severe form, might have caused death.*
- Requires inpatient hospitalization or prolongation of hospitalization – *NOTE: In general, hospitalization signifies that the patient or subject has been detained (usually involving at least an overnight stay) at the hospital or emergency ward for observation and/or treatment that would not have been appropriate in the physician's office or outpatient setting. Complications that occur during hospitalization are AEs. If a complication prolongs hospitalization or fulfills any other serious criteria, the event is serious. When in doubt as to whether "hospitalization" occurred or was necessary, the AE should be considered serious. Hospitalization for elective treatment of a pre-existing condition that did not worsen from baseline is not considered an AE.*
- Results in persistent or significant disability/incapacity – *NOTE: The term disability means a substantial disruption of a person's ability to conduct normal life functions.*

OR

- Is a congenital abnormality/birth defect.
- Is an other important medical event

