### **14.4. Data Monitoring Committee**

An independent Data Monitoring Committee (DMC) will be responsible for safeguarding the interests of the subjects by reviewing study data and providing recommendations about whether

the study is safe to proceed with ongoing enrollment as written and whether a protocol modification is required. The DMC will receive weekly updates on SAEs considered to be at least possibly related to study drug and will make a recommendation based on monthly cumulative summaries of these possibly related SAEs. The DMC will also be convened for review of available unblinded safety data and summaries of clinical data determined by the DMC to be relevant after 20 subjects have completed blinded dosing of GC4419/placebo, and may convene other meetings at its discretion. The DMC may recommend that further dosing of study treatment be discontinued and enrollment be halted pending further review if it finds that either a) more than 20% of GC4419 subjects require treatment discontinuation because of the protocol's criteria for dose reductions and discontinuation or b) the incidence of possibly related serious adverse events in the GC4419 arm constitute an unacceptable safety risk.

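### Section 10.5.1 lets an event that meets the SAE criteria be reported as a non-serious AE when judged natural progression, contradicting 10.4.2 and 10.7 and thinning the SAE counts

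*Combined protocol and SAP*

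**What the plan says.** Section 10.4.2 defines seriousness by outcome. The list begins with "Results in death", and the note on hospitalization states: "If a complication prolongs hospitalization or fulfills any other serious criteria, the event is serious". It contains no exception for disease progression.

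Section 10.5.1 opens in agreement: all events meeting those criteria "must be reported by investigational sites within 24-hours of becoming aware of the event". Its next sentence gives investigators discretion: they "may determine that the event is the natural progression of disease and therefore should be reported as an AE, but not a Serious AE". Three examples follow: worsening respiratory failure that leads to artificial ventilation, "Prolongation of hospitalization due to ventilator-associated pneumonia", and an oxygen requirement that outlasts the hospital stay. They are introduced only as examples. The revision history shows that a clarification of SAE reporting was added to this section in the latest revision, so this is current text.

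Section 10.7 still requires any AE meeting the seriousness criteria to go on the SAE form as well.

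On use of the data, 11.6 tabulates treatment-emergent, serious, severe and treatment-related AEs by subject. The Synopsis gives the DMC every SAE report. Section 14.4 is narrower: "The DMC will receive weekly updates on SAEs considered to be at least possibly related to study drug", with monthly cumulative summaries of the same events, and its criterion (b) counts only possibly related SAEs in the GC4419 arm.

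**The concern.** Seriousness describes what happened to the patient. Whether drug or disease caused it is a separate question, and the randomised placebo arm is there to answer it. The clause in 10.5.1 lets an individual judgement about cause decide the seriousness code, so part of the between-arm question is settled event by event before the arms are compared.

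This matters because the study is "intended as an initial assessment to confirm the safety of GC4419 in COVID-19 patients with critical respiratory illness". The examples are also outcomes that a harmful drug effect could resemble. Inclusion criterion 3b admits patients on non-invasive ventilation, so progression to intubation can occur after randomisation. Section 4.1.2 says that superoxide bursts, which the drug is meant to quench, "may be an essential part of the immune response to viral infection".

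At stake are consistent SAE coding across up to 10 sites and the completeness of the serious-event counts that the DMC follows between its scheduled reviews.

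**Working it through.** No figure in the plan depends on this clause, so the check compares the texts.

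**1. Is there a contradiction?** Take a patient whose stay is prolonged by ventilator-associated pneumonia.
- Under 10.4.2 the event is serious, because a complication that prolongs hospitalization is serious.
- Under the first sentence of 10.5.1 it is reported within 24 hours.
- Under 10.7 it goes on the SAE form.
- Under the second sentence of 10.5.1 and its second example, it may be reported as an AE only.

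The last instruction cannot be followed together with the first three.

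**2. Is the clause limited?** No. The examples do not bound it, death and life-threatening events are not carved out, no degree of certainty is required, and no adjudication is described. By contrast, 10.5.3 also exempts disease-related findings but overrides that exemption when the finding is more severe than expected.

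**3. Does the causality rule already protect ambiguous events?** Section 10.6 reserves the unrelated category for a high level of certainty, with a clear precipitating cause. A doubtful event should therefore be rated possibly related and reach the DMC under 14.4. The 10.5.1 clause acts at the seriousness step and has no such threshold. An event rated possibly related but called progression is no longer an SAE, so it drops out of the 14.4 feed and criterion (b).

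**4. Where does the same event appear under each reading?**

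| Place | Serious (10.4.2, 10.7) | Progression, AE only (10.5.1) |
|---|---|---|
| SAE form and 24-hour report | yes | no |
| SAE table and listing (11.6) | yes | no |
| Synopsis stream of all SAE reports to the DMC | yes | no |
| 14.4 weekly feed, monthly summaries, criterion (b) | if at least possibly related | no |
| Synopsis stopping criterion (serious or severe AEs) | yes | only if severe |
| CRF AE record with grade and relationship (10.5.2, 10.7) | yes | yes |
| All-AE table; severe-AE table if so graded (11.6) | yes | yes |
| Unblinded DMC review after 20 subjects (14.4) | available | available |
| Day-28 mortality and other endpoints (11.5) | unaffected | unaffected |

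The first four rows lose the event, the fifth can lose it, and the last four do not.

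**5. Which loss belongs to which clause?** An event judged both progression and unrelated would be outside the 14.4 feed even without 10.5.1. The loss that 10.5.1 adds is in the SAE table, in the Synopsis stream, in the Synopsis criterion for events not graded severe, and in 14.4 for possibly related events.

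**6. A second conflict found on the way.** The Synopsis and 14.4 disagree on which SAEs the DMC receives (all, or at least possibly related) and on which events count toward stopping (serious or severe, or possibly related serious).

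**The case against.** The strongest defence is that little is lost. A relabelled event is still an AE on the CRF with its grade and relationship. Severe AEs are tabulated and deaths listed separately from SAEs. The review after 20 subjects is unblinded, is not confined to SAEs and lets the DMC call for relevant clinical summaries; the DMC may also convene other meetings. The Synopsis criterion covers severe as well as serious events. The harms most feared here are measured by arm in any case, through Day-28 mortality, ventilator weaning, ventilator-free, ICU-free and vasopressor-free days, oxygenation and SOFA. All of this stands.

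A reader might therefore infer too much in four ways:
- **That these harms are hidden from the DMC, or removed before any between-arm comparison.** The routes just listed show otherwise.
- **That deaths are lost.** They are the primary endpoint, whatever the SAE label.
- **That the loss can be expressed as a fall in power.** Section 11.6 plans tabulation, not a test of SAE rates, and any power figure would rest on invented rates and relabelling shares.
- **That 4.1.2 predicts impaired infection control.** The same section goes on to say that excessive superoxide damages tissue and that converting it should not interfere with controlling the infection. The sentence quoted shows only that a harm is conceivable.

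The separate SAE manual, DMC charter and statistical analysis plan are not among the documents reviewed and may narrow the clause or widen the DMC tables. That would help in practice, but it would not remove a contradiction within the protocol or restore the ongoing SAE feed as the protocol describes it.

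**Conclusion.** The contradiction is established by the text alone: 10.5.1 conflicts with its own first sentence, with 10.4.2 and with 10.7, and is unlimited in scope. Sites can code the same event differently.

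The consequence is dilution or delay of the SAE table, the Synopsis SAE stream and the 14.4 feed and criterion (b). The documents do not fix its size. Among events meeting 10.4.2, the loss from these counts could be anything from none to every event that an investigator calls progression. Blinding makes relabelling more likely to be even between arms, but even relabelling still thins the counts in both.

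The conclusion assumes that sites use the clause as written and that the separate manual does not override it. Because the AE data, the unblinded review and the efficacy endpoints remain intact, this should be fixed but does not invalidate the safety assessment.

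**What to change.** - **Sections 10.4.2, 10.5.1 and 10.7.** Reconcile them so that seriousness coding follows 10.4.2 for every event, deaths included. Possible text for 10.5.1: *Each event meeting a 10.4.2 criterion is coded serious on the CRF, with that criterion recorded. A separate field records whether the investigator considers it disease progression (yes/no). This field may affect the expedited-reporting route only.* State explicitly how deaths and possibly related events are handled under any such exemption. Remove the ventilator-associated pneumonia example or make it consistent with 10.4.2.
- **Sections 11.6 and 14.4.** Tabulate by arm all events meeting 10.4.2, with and without those flagged as progression, for the scheduled review and for the periodic DMC summaries.
- **Synopsis and 14.4.** Reconcile which SAEs the DMC receives and which events count toward stopping. This point takes no position on which rule should prevail. Align the SAE manual and DMC charter with the result.

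The cost is protocol wording, slightly more CRF coding with one added field, and one extra DMC table. The reported SAE count will rise in both arms. If the exemption from expedited reporting is kept, that workload need not grow.

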### **10.5.2. All Adverse Events (AEs) Regardless of Seriousness**

Any adverse medical condition or laboratory abnormality with an onset date before the date of the baseline visit is considered to be pre-existing in nature, and part of a subject's medical history. Adverse medical conditions that begin on or after date of baseline visit will be considered an AE, including SAEs, and followed for 30 days after end of treatment GC4419/placebo. Similarly, new events will be reported as AEs/SAEs if the start date is within 30 Day Follow-up Period. Increases in toxicity grade of pre-existing conditions that occur on or after the date of the baseline visit are also considered an AE.

All AEs must be recorded in the patient's source documents and on the CRF regardless of frequency, severity (grade) or assessed relationship to study drug.

### **10.5.3. Clinical Laboratory Abnormalities and Other Abnormal Assessments as AEs and SAEs**

Clinically significant abnormal laboratory findings or other abnormal assessments that are associated with the disease being studied, unless judged by the investigator as more severe than expected for the patient's condition, or that are present or detected at the time of the baseline visit and do not worsen, will not be reported as AEs or SAEs.

A laboratory abnormality reported by the local laboratory may meet the criteria to qualify as an AE or SAE as described in this protocol. Laboratory abnormalities should only be recorded in the AE section of the CRF if at least one of the following criteria is met:

- Meets the criteria of an SAE

- Treatment is initiated specifically for the abnormality
- Investigational product was discontinued
- Grade 3 or Grade 4 abnormalities not present at baseline, and more severe than expected for the patient's condition in the judgment of the treating investigator

For laboratory abnormalities meeting the criteria of SAEs, the site must complete and send the SAE report including the laboratory report (as regionally required) to the sponsor using the SAE form.

Abnormal assessments (eg, ECGs) that are judged by the investigator as clinically significant will be recorded as AEs or SAEs if they meet the definitions as defined in [Section 10.4](#).

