## 4. INTRODUCTION

### 4.1. Background

#### 4.1.1. COVID-19 and Associated Respiratory Disease

Approximately 20% of people with confirmed, symptomatic COVID-19 disease, due to infection with the SARS-CoV-2 virus, will develop viral pneumonia requiring hospitalization. These patients exhibit respiratory compromise that can be characterized as severe (demonstrating dyspnea, hypoxia, and/or extensive lung opacities on chest x-ray); or critical, with respiratory failure, which may be accompanied by shock or multiorgan dysfunction). Approximately 25% of hospitalized patients, comprising approximately 5% of all patients with symptomatic infection, will have critical disease as described herein. Critical disease often manifests as a clinical picture consistent with the acute respiratory distress syndrome (ARDS), although information is still being obtained regarding the pathophysiology and pathophysiology of pulmonary compromise associated with SARS-CoV-2, compared with ARDS related to other causes. Retrospective series suggest that, after a variable initial course of disease, dyspnea begins approximately 6-7 days after the first symptoms of infection, with swift progression to frank respiratory failure/ARDS 2-3 days thereafter. Intensive care is often required for 14 days or more, and more than one attempt at ventilator weaning may be required before eventual extubation. Comorbidity among these critically ill patients includes renal, cardiac, and hepatic damage as well as hypotension requiring vasopressor treatment (Yang et al, 2020). Mortality for critically ill patients, highest among the elderly or those with significant prior concomitant conditions, has been reported to be on the order of 50-60% (Yang et al, 2020; Wu et al 2020). The IHME has recently projected that, assuming full social distancing throughout the United States through May 2020, nationwide needs for hospital beds and ICU beds will exceed national capacity (<https://covid19.healthdata.org/projections>, accessed 15 April 2020, 12 noon EDT) Further, pending effective treatments or vaccine(s), potential remains for recurrent waves of infection and the attendant needs for hospital resources.

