in inflammatory cytokines including TNFa, IL-1b & IL-6), as well as SOD data in influenza pulmonary models. The second application is in an overlapping population displaying hemodynamic instability for the treatment of hypotension refractory to vasopressor therapy, based on LPS and live E. coli challenge models. Third, emerging reports of significant kidney injury and cardiac myopathy among critically ill COVID-19 patients suggest further potential roles for GC4419 in preventing inflammatory damage to these organs, based on the known action of O2- in driving myocardial ischemia/reperfusion injury and doxorubicin cardiotoxicity, as well as cisplatin kidney injury.

For the oral mucositis indication, at the intended dose and schedule of 90 mg by 60-minute IV infusion M-F for 7 weeks, GC4419 demonstrated efficacy in the proposed indication in a randomized, double-blind, three-arm Phase 2b trial in which patients receiving standard chemoradiotherapy for locally advanced head and neck cancer received either 90 mg or 30 mg of GC4419 or placebo. GC4419 did not increase the known adverse effects of the chemoradiotherapy in this trial; the adverse event profiles for each active arm and the placebo control arm were similar.

Adverse effects attributable to GC4419 in clinical development are limited, with the principal adverse effect being mild, transient postural symptoms or hypotension at the end of the one-hour infusion, and to mild circumoral paresthesia, both attributable to transient potentiation of nitric oxide (NO). Data in humans and animals have demonstrated that these effects, which are related to Cmax, are further limited by lowering the dose or prolonging the infusion time of GC4419.

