### **9.2. Dose Delays and Dose Modifications for Toxicity**

*For any given subject, study drug infusions should not begin if the subject's mean arterial pressure (MAP) is less than 65 mmHg.*

For any given subject, hold blinded GC4419/placebo and reduce by 25% (from the initial dose) for all future infusions if:

- During infusion or within 1 hour of completing infusion, the subject experiences an acute decrease in systolic blood pressure requiring bolus fluid resuscitation OR requiring initiation of vasopressor therapy OR increased vasopressor therapy. Hold GC4419/placebo until the dose of vasopressor therapy is stable and bolus fluid resuscitation is not required.
- The subject develops serum creatinine  $> 5$  mg/dL. Hold GC4419/placebo until the creatinine is  $=< 5$  mg/dL.
- The subject develops serum total bilirubin  $> 6$  mg/dL, or AST or ALT  $> 10$  times upper limit of normal. Hold GC4419/placebo until the parameters in question are below these levels.
- The subject experiences a serious or severe adverse event considered by the investigator to be related or possibly related to blinded GC4419/placebo. Hold GC4419/placebo until the event is no longer serious or severe.

Up to two such dose reductions for a cumulative 50% from the initial dose of GC4419/placebo will be permitted for a given subject. If a subject cannot tolerate GC4419/placebo infusion after a 50% dose reduction, all dosing with GC4419/placebo for that subject will be discontinued.

Patients unable to tolerate GC4419/placebo must discontinue treatment with GC4419/placebo but should continue with other protocol assessments at the discretion of the treating investigator and with the ongoing consent of the subject.

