## **11.6. Safety Analysis**

Adverse events will be grouped by system organ class, high level term, and preferred term according to the Medical Dictionary for Regulatory Activities (MedDRA) dictionary. Incidence by subject will be tabulated for all treatment emergent, serious, severe, and treatment-related AEs. Detailed listings will be provided for all SAEs, deaths, and withdrawals due to AEs.

Laboratory measurements, vital signs, and ECG parameters will be summarized by treatment group at each of the protocol specified time points.

Further details will be provided in the trial's statistical analysis plan.

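### Section 10.5.3 leaves open whether infusion-time blood-pressure falls that trigger a dose hold are recorded as AEs, so the AE tables may under-count the drug's main known harm

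*Combined protocol and SAP*

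**What the plan says.** Section 10.5.3 opens with an exemption. It covers "Clinically significant abnormal laboratory findings or other abnormal assessments that are associated with the disease being studied", and these are not reported as AEs or SAEs "unless judged by the investigator as more severe than expected" for the patient's condition. The same section closes with a rule in the other direction: "Abnormal assessments (eg, ECGs) that are judged by the investigator as clinically significant will be recorded as AEs or SAEs", on condition that they meet the definitions in Section 10.4.

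Hypotension falls on both sides of that line. Section 4.1.1 names "hypotension requiring vasopressor treatment" among the complications of critically ill COVID-19 patients. Section 4.3 describes the drug's adverse effects as limited, "with the principal adverse effect being mild, transient postural symptoms or hypotension at the end of the one-hour infusion".

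Section 9.2 makes a pressure fall consequential for dosing. Its first criterion is an "acute decrease in systolic blood pressure requiring bolus fluid resuscitation OR requiring initiation of vasopressor therapy OR increased vasopressor therapy", during the infusion or in the hour after it. Meeting it leads to a hold and a reduction of all later infusions. The criterion does not refer to an AE record.

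For analysis, Section 11.6 says: "Incidence by subject will be tabulated for all treatment emergent, serious, severe, and treatment-related AEs". It also plans by-arm summaries of vital signs at the scheduled time points, and leaves further detail to the separate SAP.

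**The concern.** The trial is presented in the Synopsis as a first look at the drug's safety in this population, and hypotension is the harm already known. It is also the harm that a blinded investigator can most easily put down to the underlying illness. Two investigators who see the same fall, with the same fluid or vasopressor response and the same dose hold, could both point to protocol text and do different things: one enters an AE, the other does not. With about 25 subjects per arm, a few missing entries would change what the AE table says about hypotension. Blood pressure was also a live topic during the study: the revision history shows that a MAP threshold for starting infusions was added on the DMC's recommendation.

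**Working it through.** The plan gives no rate of such falls and no share attributed to disease, so there is no figure of its own to reproduce. The check is mainly a comparison of texts.

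**Does the exemption reach a pressure fall?** It can. The clause goes beyond laboratory values, and blood pressure/MAP is a scheduled assessment in Appendix 1. It need not, because the only non-laboratory example in 10.5.3 is the ECG, and a fall that needs treatment can be read as a clinical event.

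**Is there an objective trigger that forces an entry?** Not for blood pressure. The list introduced by "Laboratory abnormalities should only be recorded in the AE section of the CRF if at least one of the following criteria is met" includes treatment started for the abnormality and discontinuation of study drug, but it covers laboratory abnormalities only. It names discontinuation, not a hold or reduction. What remains for blood pressure is the judgement that the fall is worse than anticipated. That is weakest in a subject already on vasopressors, for whom a further fall may be thought unsurprising.

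**What points towards recording?**
- 10.5.1: a serious event judged to be the disease taking its course is downgraded to a non-serious AE, not dropped.
- 10.5.2: conditions that begin on or after the baseline visit, and grade increases of existing ones, are AEs.
- 10.7: clinical events are recorded whatever their link to study drug, and vital signs are a named source.
- 10.5.3, closing paragraph: recording, subject to Section 10.4, whose AE definition is broad.

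No section says which rule prevails. The exemption is the specific rule for abnormal assessments, and 10.5.2 and 10.7 are general. No text says that a fall meeting the first 9.2 criterion must be entered as an AE.

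**Would other data count the events?** Only in part.
- Blood pressure/MAP is taken before each infusion, at 30-minute intervals during it, at its end, and 1, 2 and 4 hours later (Appendix 1). Summaries by time point do not count subjects who met the criterion, and rescue treatment can restore the pressure.
- Vasopressor requirements are recorded every 12 hours while in use, so a short increase around a 3-hour infusion can be missed.
- The secondary endpoints on days free of vasopressors and on MAP below 65 mmHg would reflect sustained effects.
- Section 8.3.6 puts volume and start and stop times on the CRF but does not name the reason for a hold. Action taken with study drug is collected within the AE record (10.7), so that link is lost if no AE is entered.
- The DMC's routine updates cover possibly related SAEs, and its 20% rule counts discontinuations (14.4).

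**Illustration of size.** All incidences and shares here are assumptions.

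Observed incidence = true incidence × (1 − exempted share), with the same share in both arms:

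| Exempted share | GC4419 | Placebo | Difference | Ratio |
|---|---|---|---|---|
| 0 | 0.50 | 0.20 | 30 points | 2.5 |
| 0.5 | 0.50 × 0.5 = 0.25 | 0.20 × 0.5 = 0.10 | 15 points | 2.5 |
| 0.8 | 0.50 × 0.2 = 0.10 | 0.20 × 0.2 = 0.04 | 6 points | 2.5 |

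The last row is 2.5 against 1 subject of 25.

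With lower assumed incidences on GC4419, expected subjects in the table = 25 × incidence × recorded share. The chance that none appears = (1 − incidence × recorded share)^25, treating subjects as independent:

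| Incidence | Recorded share | Expected | Chance of none |
|---|---|---|---|
| 20% | 1 | 5 | 0.80^25 = 0.4% |
| 20% | 0.5 | 2.5 | 0.90^25 = 7.2% |
| 20% | 0.25 | 1.25 | 0.95^25 = 27.7% |
| 40% | 1 | 10 | below 0.1% |
| 40% | 0.5 | 5 | 0.80^25 = 0.4% |
| 40% | 0.25 | 2.5 | 0.90^25 = 7.2% |

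**The case against.** The best defence is that the protocol, read as a whole, favours recording. Section 10.5.1 shows its approach to disease-attributed events: reclassify, do not omit. A fall that needs fluid or a vasopressor fits 10.5.2 and 10.7 better than a clause on abnormal assessments. When it is timed to an infusion of a drug with anticipated infusion hypotension (Section 9.1), it is an awkward candidate for attribution to disease. Many investigators would record it. This stands, and it is why the point is one of inconsistency and not of instructed omission.

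A reader might infer that the two ends of 10.5.3 flatly contradict each other. They do not: the closing rule is conditional on Section 10.4 and the opening one has an exception. They overlap on the same event without an order of precedence.

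A reader might also infer that the trial could report little hypotension for a drug that repeatedly needed vasopressor rescue. The documents do not support that either. Sustained rescue would show by arm in the vasopressor endpoint and the vital-sign summaries, and the DMC sees unblinded safety data. What these sources lack is a count of subjects and infusions meeting the 9.2 criterion.

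The separate SAP may already contain a table of holds and reductions. Its text is not part of the document reviewed, so the absence of one from 11.6 proves little. An SAP table would still depend on these events being captured at the site.

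Finally, the illustration rests on assumed inputs. Section 4.3 calls the effect mild and transient, and the infusion was lengthened to limit it. If the same share is unrecorded in both arms, the relative risk is unaffected.

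**Conclusion.** The point holds as a reporting ambiguity that should be resolved. The opening of 10.5.3 allows a disease-associated pressure fall to go unrecorded, other sections lean the other way, and nothing settles the matter for the event that is both a disease feature and the main known toxicity. The consequence is possible inconsistent recording and an under-count in the AE tables, which would shrink the absolute excess on GC4419. The extent is unknown: it depends on how often such falls occur and how sites read the clause, and the documents inform neither. The stronger conclusion, that the plan excludes these events or would hide the signal altogether, is not supported.

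**What to change.** In 10.5.3, state that the disease-association exemption does not apply to a pressure fall that meets the existing first criterion of 9.2, and that each such fall is recorded as an AE whatever its presumed cause. Align the opening and closing paragraphs of 10.5.3 with 10.5.1, 10.5.2 and 10.7 accordingly.

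In 11.6, or in the separate SAP, add one table by arm: subjects with at least one such event, and events per infusion given. The second denominator matters because subjects whose dosing is held receive fewer than the planned infusions (2 a day × 7 days = 14).

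The 9.2 dosing rules are untouched. Sites must already recognise each event to apply 9.2, and infusion details are already on the CRF, so the cost is one sentence, one table and a few more AE entries in both arms.
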